7.2.2.2. Dose Escalation Method

[Table JBDA 7.1.](#) outlines the proposed dose-escalation scheme. In this study, the escalation will start from the lowest planned dose, the maximum allowed dose increment is 100%, and each new dose level will have a minimum of 3 patients enrolled to it. The Bayesian model-based toxicity band method (Neuenschwander et al 2008) that incorporates prior expectations about the dose-toxicity curve will be fitted to the data at the end of each cohort to recommend a dose for the next cohort. The toxicity band method is a Bayesian model-based design with built-in escalation with overdose control mechanism. After each cohort, the toxicity band model will utilize data from all available cohorts to make dose recommendation, based on the model based posterior probability of a DLT at each dose, and the overdose control criteria. The toxicity band method will stop if the pre-specified maximum number of subjects is reached or the recommended next dose has been taken by 9 patients.

During the escalation, the investigators and Lilly CRP will consider both the model recommendation and the observed DLT rate at each cohort to determine the next dose level and determine when to stop the escalation. Dose levels for each cohort will not exceed those recommended by the toxicity band model. Dose escalation will take into account PK and PD information when available. Additional patients may therefore be enrolled at a specific dose level to characterize PK/PD.

Intermediate or higher dose levels will be explored if deemed necessary after discussion between the sponsor and investigators. The JBDA toxicity band model has the ability to accommodate additional dose levels naturally.

Details regarding the JBDA toxicity band design are provided in [Attachment 10](#).

Table JBDA 7.1. Proposed Dose Escalation Scheme

Dose level	LY3009120 Dose (given BID) (mg)	Predicted Median AUC _{0-τ,ss} (ng*h/mL)	Predicted 5th and 95th percentiles AUC _{0-τ,ss} (ng*h/mL)	Predicted Median C _{max,ss} (ng/mL)	Predicted 5th and 95th percentiles C _{max,ss} (ng*h/mL)
1	50	1320	571-2560	139	63-250
2	100	2250	989-4550	232	108-442
3	200	2620	1150-5050	272	125-499
4	300	2770	1220-5310	290	140-528
5	400	3230	1440-6250	339	160-618
6	500	3780	1670-7460	393	187-750
7	600	3840	1630-7690	407	182-773
8	700	3980	1770-7780	419	201-771

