1.2 Toxicity Band design

All the aforementioned approaches use point estimates of the posterior distributions to recommend the next dose. Neuenschwander et al. (2008) extended the concept of EWOC and proposed to consider the uncertainty of the posterior distributions and use interval estimates to make the dose recommendation. We call their approach the Toxicity Band Design.

The Model

A two-parameter logistic model is used to model the relationship between dose and probability of a DLT:

$$\text{logit}\{p(d)\} = \alpha + \beta \log\left(\frac{d}{d^*}\right), \quad \beta > 0. \quad (1.1)$$

In the model, d is the true dose, $p(d)$ is the probability of a DLT at dose d . d^* is the reference dose such that α is interpreted as the log-odds of a DLT at d^* .

Toxicity Band

The probability of a DLT is categorized to four bands:

Under-dosing: $p(d)$ in $(0, 0.20]$

Targeted toxicity: $p(d)$ in $(0.20, 0.35]$

Excessive toxicity: $p(d)$ in $(0.35, 0.60]$

Unacceptable toxicity: $p(d)$ in $(0.60, 1.00]$

The over-dosing means $p(d) > 0.35$.

MTD Definition

The MTD is defined as a safe dose that has the highest probability of DLT in the targeted toxicity interval (20 to 35%). A safe dose means that the probability of DLT larger than 35% is below 25%.

Dose Recommendation

During the escalation, after each cohort of patients, we

- 1) Calculate the posterior probabilities of the four toxicity bands, for each dose.
- 2) Exclude the doses such that the posterior probabilities of over-dosing are larger than 0.25 (JBDA over-dosing control criteria). The remaining doses are the ones that satisfy the overdose control criteria.
- 3) Among the remaining doses, the dose with the highest posterior probability in the targeted toxicity band will be the model recommendation of the next dose.

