1.5 Simulation Studies

We perform simulations under different scenarios to investigate the operational characteristics: Toxicity band method vs. traditional 3+3.

- 3-patient cohorts starting from the lowest dose. No dose skipping.
- Maximum number of patients: 33
- Stopping rules for Tox-band method: max sample size reached or the recommended next dose has been treated for 9 Patients:

We considered 8 scenarios to represent a wide range of possible curves. The true DLT rate of the MTD is fixed at 25% across scenarios. Scenario 1 and 2 are toxic cases that have MTD at the first and second level. Both scenario 3 and 4 (in blue color) have 300 mg at the MTD with either steep or flat curves. Similarly, we design scenario 5 and 6 to have the same MTD at 400 mg. Scenario 7 has MTD at 500 mg, whereas scenario 8 is a safe case that the MTD is at the last dose.

[figure not shown]

Figure 3. The Pre-specified probability of DLT under each scenario

Table 2. The Pre-specified probability of DLT under each scenario

	Pre-specified Prob. of DLT							
Dose	1	2	3	4	5	6	7	8
50	0.25	0.14	0.07	0.02	0.03	0.01	0.05	0.01
100	0.4	0.25	0.09	0.04	0.05	0.03	0.07	0.02
200	0.55	0.40	0.13	0.09	0.09	0.05	0.11	0.05
300	0.65	0.55	0.25	0.25	0.14	0.09	0.14	0.08
400	0.75	0.65	0.36	0.47	0.25	0.25	0.17	0.11
500	0.85	0.75	0.48	0.65	0.36	0.5	0.25	0.15
600	0.90	0.85	0.60	0.80	0.47	0.65	0.40	0.18
700	0.95	0.90	0.75	0.90	0.60	0.80	0.55	0.25

We ran 1000 simulations under each scenario to investigate the operating characteristics of the Toxicity Band and 3+3 methods. The results are summarized in Table 3 and 4.

Table 3. Probability of each dose selected as MTD, mean number of subjects, and mean percentages of a DLT under each scenario: Results based on 1000 simulations (Toxicity Band Method)

Dose	Scenarios							
	1	2	3	4	5	6	7	8
50	0.833	0.422	0.084	0.008	0.015	0.002	0.031	0
100	0.159	0.464	0.159	0.068	0.072	0.019	0.138	0.018
200	0.008	0.109	0.247	0.333	0.105	0.047	0.121	0.038
300	0	0.005	0.342	0.512	0.274	0.313	0.126	0.093
400	0	0	0.136	0.076	0.337	0.527	0.204	0.120
500	0	0	0.028	0.003	0.152	0.086	0.233	0.138
600	0	0	0.003	0	0.027	0.005	0.095	0.137
700	0	0	0.001	0	0.018	0.001	0.052	0.456
Mean # of Subj.	10.035	14.358	21.585	22.479	25.020	25.710	25.266	28.977
Mean % of a DLT	39.20	27.54	19.57	17.62	16.26	15.73	15.93	10.79

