Table 4. Probability of each dose selected as MTD, mean number of subjects, and mean percentages of a DLT under each scenario: Results based on 1000 simulations (3+3 Method)

Dose	Scenarios							
	1	2	3	4	5	6	7	8
50	0.808	0.504	0.133	0.020	0.035	0.008	0.071	0.009
100	0.164	0.344	0.125	0.069	0.080	0.022	0.099	0.023
200	0.028	0.135	0.302	0.389	0.167	0.083	0.153	0.057
300	0	0.017	0.282	0.417	0.295	0.353	0.147	0.090
400	0	0	0.135	0.097	0.269	0.458	0.222	0.135
500	0	0	0.021	0.008	0.118	0.074	0.213	0.162
600	0	0	0.002	0	0.032	0.002	0.076	0.203
700	0	0	0	0	0.004	0	0.019	0.321
Mean # of Subj.	7.605	10.251	16.203	16.554	19.356	19.488	20.331	24.696
Mean % of a DLT	38.76	28.91	19.26	16.95	15.55	14.61	15.93	9.97

From the results, we can see that, in terms of MTD estimation accuracy, the Toxicity band method successfully identified the correct MTD with the highest selection percentages under each scenario, whereas 3+3 failed to identify the correct MTD with the highest selection percentages at half of the scenarios. The MTD determination based on 3+3 algorithm is generally one level lower than the true MTD. Moreover, in general, the Toxicity band method has a higher correct MTD selection percentage than the 3+3 design, under each scenario.

In terms of the mean number of subjects, the Toxicity band typically needed 4 to 6 more patients compared to the traditional 3+3. The mean percentages of a DLT are in general comparable across two methods, which indicates that the Toxicity band method is conservative and safe.

In sum, from the simulation studies, the Toxicity band method has a better MTD estimation accuracy, and a comparable safety profile, compared to the traditional 3+3 design.

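### Tables 3 and 4 have no no-MTD outcome, so the scenario 1 rates (0.833 and 0.808) are not correct-selection rates and do not support superiority there

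*Protocol*

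**What the plan says.** Attachment 10, section 1.2, sets the dose rule in two steps. First: "Exclude the doses such that the posterior probabilities of over-dosing are larger than 0.25 (JBDA over-dosing control criteria"). Then: "Among the remaining doses, the dose with the highest posterior probability in the targeted toxicity band will be the model recommendation" of the next dose. The MTD must be a safe dose, and "A safe dose means that the probability of DLT larger than 35% is below 25" percent. Nothing says what happens when the first step removes all eight doses.

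Section 1.5 describes the simulations: "3-patient cohorts starting from the lowest dose. No dose skipping", at most 33 patients, and "Stopping rules for Tox-band method: max sample size reached or the recommended next dose has been treated for 9 Patients". Protocol 7.2.2.2 and SAP 5.3.2 give the same two stopping rules: the method "will stop if the pre-specified maximum number of subjects is reached or the recommended next dose has been taken by 9 patients". Protocol 7.2.2.2 adds that "Dose levels for each cohort will not exceed those recommended by the toxicity band model", and refers undescribed situations to the investigator and the sponsor physician, with the decision documented in writing.

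Tables 3 and 4 list selection probabilities for the eight doses only. For scenario 1, where 50 mg is the true MTD, they print 0.833 (toxicity band) and 0.808 (3+3) at 50 mg. The text then states that "in general, the Toxicity band method has a higher correct MTD selection percentage than the 3+3 design, under each scenario", and that 3+3 fails to favour the true MTD in half of the scenarios.

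**The concern.** Any dose-finding method can conclude that its lowest dose is too toxic. In scenario 1 the true DLT rate at 50 mg is 0.25, so small cohorts will often reach that conclusion. Such a trial has no MTD. If it is entered in the 50 mg row, then in scenario 1 a failure to find a dose is reported as a correct answer.

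These tables are the stated evidence for the method that serves the primary objective. A reader of the protocol takes from them that about 83% of toxicity band trials identify the right dose when the drug is toxic at the starting level. That is also where a pre-specified action matters most for patients.

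**Working it through.** **Inputs.** True DLT rates from Table 2; selection rates and mean numbers of patients from Tables 3 and 4; the prior from section 1.4 (means −0.092 and 0.359, SDs 2.507 and 0.907, correlation 0.282); reference dose 700 mg from section 1.3. The protocol does not spell out its 3+3 variant. I assume the usual one: a dose passes with 0/3 or 1/6 DLTs, fails with two or more, and the MTD is the highest dose passed.

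**1. Column sums.** All 16 columns sum to 1.000. For scenario 1: Table 3, 0.833 + 0.159 + 0.008; Table 4, 0.808 + 0.164 + 0.028. There is no room for a no-MTD outcome.

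**2. Exact 3+3 (Table 4).** With q = 1 − p, a dose passes with probability e(p) = q³ + 3pq⁵.
- e(0.25) = 0.422 + 0.178 = 0.600; e(0.40) = 0.216 + 0.093 = 0.309.
- Scenario 1, no MTD: 1 − 0.600 = 0.400.
- Scenario 1, valid 50 mg: 0.600 × (1 − 0.309) = 0.414.

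| Scenario | Valid 50 mg | No MTD | Sum | Table 4, 50 mg row |
|---|---|---|---|---|
| 1 | 0.414 | 0.400 | 0.814 | 0.808 |
| 2 | 0.334 | 0.166 | 0.500 | 0.504 |
| 3 | 0.074 | 0.050 | 0.124 | 0.133 |
| 4 | 0.017 | 0.005 | 0.022 | 0.020 |
| 5 | 0.026 | 0.010 | 0.036 | 0.035 |
| 6 | 0.010 | 0.001 | 0.011 | 0.008 |
| 7 | 0.048 | 0.027 | 0.075 | 0.071 |
| 8 | 0.005 | 0.001 | 0.006 | 0.009 |

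The sum matches the printed row within 0.01 in all eight scenarios. In scenario 1, valid selections alone (0.414) do not match 0.808. Dropping the failures and rescaling does not match either (0.414/0.600 ≈ 0.69).

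In scenario 2 the exact 3+3 rate at the true MTD of 100 mg is 0.345 (printed 0.344). Against 0.334 valid selections of 50 mg, 3+3 no longer favours 50 mg.

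**3. Can the model exclude every dose?** Posterior P(p > 0.35), data at 50 mg only:

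| DLTs at 50 mg | At 50 mg | At 100 mg |
|---|---|---|
| 1/3 | 0.259 | 0.45 |
| 2/3 | 0.712 | 0.86 |
| 2/6 | 0.304 | 0.57 |
| 3/9 | 0.324 | 0.64 |

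Higher doses are worse still. After 2/3, 2/6 or 3/9 no dose passes 0.25; after 1/3 the same holds, but only marginally. In these states 50 mg does not meet the MTD definition.

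**4. Do the written stopping rules give Table 3's mean N?** Under those two rules a scenario 1 trial needs at least 9 patients. After 0/3 at 50 mg the model recommends a higher dose, so at least 3 patients are treated at another dose and the trial needs at least 12. Hence mean N ≥ 9 + 3 × 0.75³ = 9 + 3 × 0.422 = 10.27. Table 3 prints 10.035. The Monte Carlo SE of this minimum over 1000 trials is 3 × √(0.422 × 0.578/1000) = 0.047, and (10.266 − 10.035)/0.047 = 4.9. Some trials stopped earlier than the written rules allow.

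**5. How large is the Table 3 share?** The rule is unstated, so these are assumed actions when no dose passes. Scenario 1, 40,000 simulated trials for each of the first three; the last is a separate run:

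| Assumed action | Valid 50 mg | No MTD | Sum (printed 0.833) | Mean N (printed 10.035) |
|---|---|---|---|---|
| Stay at 50 mg to 9 patients | 0.417 | 0.386 | 0.804 | 12.5 |
| Stop, except after 1/3 in first cohort | 0.273 | 0.529 | 0.803 | 10.5 |
| Stop at once | 0.168 | 0.668 | 0.836 | 7.8 |
| Stay at 50 mg to 33 patients | 0.69 | 0.10 | 0.79 | – |

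No rule reproduces Table 3. The second is closest overall.

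In scenario 2 the first three rules give 0.499, 0.497 and 0.397 at 100 mg, against 0.345 for exact 3+3.

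**The case against.** The superiority sentence is hedged and agrees with the printed tables; no sum in them is wrong. For conduct, an MTD must be a safe dose, so if none is safe there is none. Doses may not exceed the model's recommendation, which can be read as an instruction to stop. Undescribed situations go to the investigator and sponsor physician, and the sponsor may stop the study. Scenario 1 is a deliberately toxic case, whereas the prior median DLT rate at 50 mg is 0.005. The simulator's settings are not in the documents, so Table 3 cannot be reconstructed.

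Much of this stands. Conduct is governed by judgement, so what is missing there is a pre-specified action. The folding in Table 3 is inferred, not proved. The general case for the toxicity band does not rest on scenario 1. But a clause on conduct cannot correct tabulated rates, and agreement with the printed tables is no defence when the table entry is not the quantity that the sentence names.

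Two stronger readings are tempting. A reader might infer from the first three assumed rules that between 39% and 67% of scenario 1 trials end with no MTD. That is not a bound: two of those rules miss the printed mean N by more than 2 patients, and the fourth, which the text also allows, gives 0.10. A reader might also infer that the toxicity band is at best equal to 3+3 in scenario 1, by setting its valid rate against 0.414. That compares a posterior-probability standard with a DLT-count standard, and again depends on a rule nobody has written.

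**Conclusion.** The point holds, in three degrees of certainty.

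- **Shown, for Table 4.** The 50 mg row includes trials that found 50 mg too toxic. In scenario 1 they make up about half of the printed 0.808 (0.400 of 0.814 in the exact calculation) and count as correct. This assumes only the usual 3+3 rules, which reproduce the 50 mg row in all eight scenarios.
- **Very probable, for Table 3.** Its columns also leave no room for a no-MTD outcome, the model readily reaches a state with no admissible dose, and the printed mean N implies an undisclosed early stop.
- **Not recoverable.** The closest assumed rule puts about half of all scenario 1 trials in the no-MTD group, but the figure depends on the unwritten rule and no range should be claimed.

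So 0.833 and 0.808 are not correct-selection rates, and the claim of a higher correct rate under every scenario is unsupported in scenario 1. The tables cannot show which method is better there. In scenario 2 the toxicity band's advantage at 100 mg is not overturned, but 3+3 moves from favouring 50 mg to a near tie (0.334 against 0.345 at 100 mg), so the count of scenarios in which 3+3 fails needs review.

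**What to change.** State the early-stop rule that was active in the simulations. In protocol 7.2.2.2, SAP 5.3.2 and Attachment 10, state the action when no dose meets the 0.25 criterion: for example, continue at 50 mg to a stated number of patients, open a lower dose, or stop and declare no MTD. Re-run Tables 3 and 4 under that rule with a separate no-MTD row. Restate the scenario 1 and 2 rates and the count of scenarios in which 3+3 fails. Limit the superiority sentence to the scenarios that the re-run supports, and leave scenario 1 open until then.

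The cost is one re-run of an existing simulation, wording changes, and less favourable stated rates in the toxic scenarios. The prior, the overdose criterion and the MTD definition stay as they are.

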1.6 Dose confirmation Phase

The MTD identified in the escalation phase will continue to be evaluated by the model during the dose confirmation. For each confirmation cohort, about 15 patients will be enrolled to ensure adequate safety evaluations.

Attachment 11. Protocol JBDA Protocol Amendment I6X-MC-JBDA(d) Summary A Phase 1 Study of LY3009120 in Patients with Advanced or Metastatic Cancer

Overview

Protocol I6X-MC-JBDA, a Phase 1 Study of LY3009120 in Patients with Advanced or Metastatic Cancer, has been amended. The new protocol is indicated by Amendment (d) and will be used to conduct the study in place of any preceding version of the protocol.

The overall changes and rationale for the changes made to this protocol are as follows:

- Added statement around previously generated genetic data to Section 5.3.4 such that these data may be requested from medical records for use in the research described in Section 5.3.4.3.
- Section 5.3.4.3. was updated to clarify that exploratory biomarker analysis will be performed on patients enrolled in *all cohorts* in Part B and not just in Cohort A. This was also updated in the inclusion criterion [3] for Part B.
- Section 8.2.4.1: added statement regarding mandatory tumor biopsies before treatment and 2 weeks after treatment for all patients in Part B.
- Requirement of archived tissue for Part B is removed from Section 8.2.4.2 and from the Part B Baseline Assessment schedule.
- Updated Attachment 1, Part B Baseline Assessment schedule to include study tumor biopsy for all cohorts.
- Updated Attachment 1, Part B During and Poststudy Assessments to include tumor biopsy at Day 15, removed PK sampling at Day 28 Cycle 1, and included PK sampling for Day 28 Cycle 2 and beyond to keep it consistent with the information in Attachment 4. Text was also added for eye assessments, such that the Day 28 assessment can also be performed on the Day 1 of the next cycle (predose).
- Updated Attachment 4, Pharmacokinetic Sampling Schedule For Patients in Part B, to remove Cycle 1 Day 1 10 hour PK sampling time, added exploratory blood sampling at Cycle 1 Day 22, and removed all PK samplings at Day 28 for Cycle 1.
- Other minor formatting changes and changes to text were made for consistency and clarity.

Revised Protocol Sections

Note: All deletions have been identified by ~~strikethroughs~~.
All additions have been identified by the use of underline.

5.3.4. Biomarkers

As part of an ongoing effort by Lilly to better understand how to predict which tumors are more likely to respond to LY3009120 treatment, the collection of samples for biomarker research is a mandatory part of this study. Additional details about sampling are summarized in Sections 8.2.4 and 8.2.5, Attachment 1, Attachment 4, and Attachment 8.

It is possible that biomarker data for patients in the study have already been generated from samples that were collected and analyzed before enrolling in this trial. These may include data generated from genetic analyses. If available, these data may be requested from medical records for use in the research described in Section 5.3.4.3.

5.3.4.3. Exploratory Analysis of Predictive Biomarkers

Potential predictive biomarkers of efficacy to LY3009120 will be measured in archived tumor tissue, tumor tissue from core or excisional biopsies, and plasma. Core or excisional biopsies for exploratory biomarker analysis will be performed on patients enrolled in all cohorts in Part B Cohort A (see Section 6.1.1 Inclusion ~~Criteria~~ Criterion [3]) before receiving the first dose of study drug, but this will not delay treatment. Exploratory biomarker analysis may be performed on preexisting archival samples from patients in Part A and Part B. The predictive biomarkers to be studied may include, but not limited to, somatic alterations in cancer-related genes such as B-Raf, NRas, KRas, and cKIT. In plasma, analysis of biomarkers may include, but not limited to, potential nucleic acid predictive profiles to better understand the disease process and to develop predictive biomarkers.

6.1.1. Inclusion Criteria

Patients may be included in the study if they meet **all** of the following criteria during screening prior to first dose of study drug.

...

- [3] ~~Part A and Part B Cohort A:~~ Have a tumor that is safely amenable to core needle or excisional biopsies

- [8] Have discontinued all previous therapies for cancer (including chemotherapy, immunotherapy, corticosteroids, and radiotherapy) and recovered from the acute effects of therapy (treatment related toxicity resolved to Grade 1 or less) for at least 5 half-lives or a ~~maximum~~minimum of 4 weeks, (at least 42 days for mitomycin-C or nitrosoureas, 14 days for radiotherapy), prior to initiating study treatment.

8.2.4.1. Tissue Collection for Pharmacodynamic Studies

Part A: **Mandatory** tumor biopsies should be collected prior to treatment (following determination of eligibility [≤ 14 days of C1 D1]) and after 4 weeks of treatment (C1 D28 \pm 14 days) for patients added to any cohort that will be expanded to determine MTD and/or for patients added to any cohort expanded to explore potential for Phase 2 dosing on the basis of PK data. Biopsy samples taken within 6 months prior to enrollment will also be permitted as long as patients have not received any recent therapies for the disease prior to starting LY3009120. Sponsor will need to review and approve the timing of in-treatment biopsies performed outside of the allowed 14-day window.

Part B: **Mandatory** tumor biopsies should be collected before treatment (following determination of eligibility [≤ 14 days of C1 D1]) and after 2 weeks of treatment (C1 D15 \pm 5 days). Biopsy samples taken within 6 months before enrollment will also be permitted as long as patients have not received any recent therapies for the disease prior to starting LY3009120.

Tumor tissue biopsies taken either by core needle or excisional biopsy are acceptable provided adequate slides can be obtained. Cytologic samples and fine-needle aspiration specimens are not acceptable. Pathology notes accompanying the archived diagnostic tissue may also be requested.

Details for the handling and shipping of tumor biopsy samples will be provided in a separate document. Instructions and supplies required for the collection, processing, and shipment of the patients' samples will be provided by the sponsor.

The tumor tissue samples will be coded with the patient number and stored for up to a maximum of 15 years after the last patient visit for the study at a facility selected by the sponsor.

